The main objective of this clinical trial is to test the efficacy of two different transcranial electrical stimulation techniques (tES) to modify dysfunction of central modulatory mechanisms of pain, and to improve symptoms and quality of life in refractory chronic pain patients.

In this vein, we hypothesize that transcranial electrical stimulation procedures will be more effective than sham to improve pain and related symptoms. Besides, central biomarkers of pain processing and modulation (i.e., CPM, TSSP and EEG) will be useful to predict the patient response to treatment and thus, the efficacy of these tES procedures.

Based in these principal ideas, we propose the following secondary or specific objectives:

- A. To analyse the relationship between the studied biomarkers and clinical pain characteristics of patients (intensity, location, frequency, duration, daily interference caused by pain).
- B. To stratify patients and propose profiles based on the selected biomarkers, which may be useful to improve diagnosis and to guide individualized treatment plans.
- C. To develop home-based treatment schemes for patients with refractory chronic pain. We will assess if tES procedures are safe, feasible and acceptable for the at-home management of this medical condition.
- D. To test if tES techniques are self-manageable by patients and to observe the impact of this treatment in the caregiver-burden declared by the reference person.
- E. To test the efficacy of tDCS (Direct current) versus tACS (Alternant current) to modify dysfunction of central endogenous analgesia (i.e., CPM and TSSP) and to reduce pain and related symptoms in the patients, in a placebo-controlled clinical trial.
- F. To analyze how the different tES techniques (tDCS and tACS) affect brain oscillatory activity, and to test if the changes in oscillatory activity are related to pain relief.
- G. To test the power of the biomarkers/patients' stratification to predict treatment efficacy and to identify the characteristic of best responders patients.

- H. To assess the effect of sex/gender and other modulator variables (age, disease duration, medication, lifestyle, mood...) on all the analyses (central biomarkers, patients' stratification, response to treatment...).

3. Study design

The research is classified as a double-blinded, randomized clinical trial with one control group which receive a sham stimulation.

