The transcranial electrical stimulation intervention is considered the independent variable, which contains three different conditions or categories differentiated by the type of stimulation used. These conditions define the three groups of treatment:

- 1) Transcranial direct current stimulation (tDCS), which induces a continuous current over the left primary motor cortex (M1). Current intensity is set at 2mA and it is applied for 20 minutes, with ramp-up and ramp-down of 15 seconds at the beginning and end of the stimulation period.
- 2) Transcranial alternat current stimulation (tACS), which induces an alternant current over somatosensory cortical region. Current intensity is set at 10-Hz and it is applied for 20 minutes, with ramp-up and ramp-down of 15 seconds at the beginning and end of the stimulation period.
- 3) Sham stimulation, which acts as a placebo-control group. It uses the same montage as the previous ones, but it does not emit any kind of current. The position of electrodes will be similar to the previous conditions, but the current will be just activated during the ramp-up and ramp-down moments.

Chronic pain patients are randomly assigned to one of these groups, although the active stimulation conditions agglutinate the 80% of sample (40% tDCS; 40% tACS), whereas the control group contains by the remaining 20%.

As dependent variables, we consider the assessed clinical symptoms, mainly pain characteristics (including intensity, location, frequency, duration and daily interference caused by pain), fatigue, depression/anxiety, sleep quality, physical functioning and life quality, following the guidelines proposed by the *Initiative on Methods, Measurement, and Pain Assessment in Clinical Trials* (IMMPACT; Dworkin et al., 2005).

Besides, as far as we aim to assess the efficacy of tES techniques to restore the potential dysfunctions in processing and modulation of pain in patients, central biomarkers as Conditioned Pain Modulation (CPM), Temporal Summation of Second Pain (TSSP) and EEG are also included as dependant variables. Thus, we try to identify any change in these variables which could be attributable to the intervention.

The intervention and evaluation protocols are more in-depth defined in the following sections.

4. Sample and recruitment

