Epidemiological studies have consistently reported higher prevalence rates of chronic pain syndromes among women, compared to men (Jiménez-Trujillo et al., 2019; Cimas et al., 2018). As we intend to create a feasible and useful tool for clinical practice, these gender differences must also be considered when designing the recruitment plan and deciding the sex distribution of the sample. As we aim to assess the influence of sex/gender in tDCS treatment efficacy and central pain modulation mechanisms, we will recruit both male and female patients, although the latter will represent about 70% of the total sample, in accordance with clinical reality; whereas males will represent at least the 30% of the selected patients, in order to improve and facilitate subsequent comparative analysis. The **inclusion criteria** applied for the selection of patients are the following:

- Suffering a chronic pain condition of non-cancer nature. Those patients who report chronic pain even after overcoming an oncological process are suitable to participate, but only if they have received the definitive medical discharge and have been free from radiotherapy/chemotherapy for at least twelve months.
- Adult subjects (18-65 years old).
- Subjects able to provide informed consent to participate in the study and to self-report pain.
- Existing chronic pain which reaches an intensity of at least 4 on a 0-10 Numeric Rating Scale (NRS) on average over the past 3 months prior to enrolment.
- Pain intensity of at least 5 on a 0-10 NRS over the week prior to enrolment.
- Diagnosis of pharmaco-resistance to analgesic drugs across the WHO ladder.

Participants are allowed to continue with their usual pharmacological regimen, but it must have been stable during the two months previous to the enrolment, and it must not suffer modifications during the whole research period. We will account for the potential effects of some drugs over the efficacy of tDCS/tACS treatment (McLaren et al., 2017), making a registry of patients pharmacological prescriptions to consider them in further

analysis. Rejecting patients who consume medicaments which can apparently interfere with tDCS/tACS effects would not be a well-balanced alternative and would result in a huge loss of participants, since some of these drugs are included as priority treatment for many chronic pain conditions. As far as the **exclusion criteria** are concerned, they are exposed below:

- Chronic pain derived from current cancer disease.

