Besides, we will conduct simple ANOVA analyses to compare these indexes of pain processing and modulation (CPM, TSSP, EEG) between specific groups of patients, divided by type/origin of chronic pain and sex. We reserve the possibility of making *Cluster analyses* in the basis of the mentioned central biomarkers, following by an ANOVA comparison of clinical features between the emerged groups.

Besides, participants will be classified into CPM and TSSP respondents or non-respondents taking into account their results in these sensory tests. Those patients who report a significant increment in pain thresholds will be considered respondents; whereas the opposite applies for TSSP, as it must be detected a significant increase in perceived pain intensity in the last pulse compared to the first one. Depending on the proportions observed, it could be useful to divide TSSP respondents based on the degree of the pain sensitization. Regarding this sample division, we can compare the clinical profile of respondents and non-respondents patients using *Chi square statistic*.

As far as intervention efficacy is concerned, qualitative analyses will focus on differentiating the patients who effectively respond to treatment (Treatment-respondents) from those who do not improve (Non-treatment-respondent). Respondents are those

participants whose improvement in a certain clinical variable are equal or higher than the 30%; whereas non-respondents are all those who do not comply with this criterion. This variation is extracted from the comparison of pre- and post-treatment measurements.

Therefore, for each of the endpoints, we will obtain a number/percentage of respondents and non-respondents. Using the *Chi-square test*, we will compare the proportion of respondents between treatment groups to identify the most efficacious stimulation procedure. A separated analysis will be done for each described endpoint, which define what a respondent is.

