The main quantitative statistical analyses to assess the efficacy of transcranial electrical stimulation techniques consist of ANOVA-tests of repeated measures with three groups. Time-measures for each of the above-mentioned endpoints are taken as intragroup variables (pre vs. post), whereas intergroup measures refer to the received stimulation or treatment (tDCS vs. tACS vs. Sham). Thus, both clinical variables (for example, pain intensity, fatigue, sleep quality, disease severity and interference) and potential biomarkers (including brain oscillatory activity registered by EEG, CPM and TSSP response) are considered as intragroup variables.

Those covariates which show a significant correlation with clinical outcomes will be also included in their correspondent ANOVA analysis. These potential covariates are basically age, self-perceived stress, social support, catastrophism and medication intake.

All these statistical analyses will be repeated in separated groups of patients, created in the basis of sex, type and duration of chronic pain, among other characteristics. The objective is to assess whether the clinical outcomes depend on sex or diagnosis, as each tES could be more effective for specific diseases.

CPM/TSSP response and EEG pattern observed before the tES application are also regarded as potential predictors of the treatment efficacy. Thus, the pre-treatment indexes of these biomarkers will be used as independent variables in *Linear regression models*, which includes the clinical improvement in each endpoint as dependent measure. The procedure will be repeated with *Logistic regression analysis* establishing the respondent vs. no-respondent categories as dichotomic variable.

For last, we will register and assess the percentage of dropouts with their respective motives, in order to obtain an index of the feasibility of home-based tES approach. Client

satisfaction index and caregiver interview will also include questions about the capability of participants to manage with tES devices, data which will be qualitatively analysed.

8. Chronogram

WORKING PLAN (WP)		3	6	9	12	15	18	21	24	27	30	33	36
TASK	\ MONTH												
WP1. Development and selection of assessment and monitoring tools for refractory chronic pain patients													
Task 1.1.	Review of the literature and identification of the most common and important variables used as outcomes in clinical trials with chronic pain population.												

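### Whether the treatment effect differs by sex, pain type or duration is to be judged by repeating the analyses in separate groups; no arm-by-subgroup interaction test is planned.

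*Combined protocol and SAP*

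**What the plan says.** Section 7 gives one method for effect modification: "All these statistical analyses will be repeated in separated groups of patients, created in the basis of sex, type and duration of chronic pain", followed by an open-ended reference to further characteristics. The next sentence gives the purpose: "The objective is to assess whether the clinical outcomes depend on sex or diagnosis, as each tES could be more effective for specific diseases".

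The question is a declared aim of the trial:

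- Objective H in Section 2 begins "To assess the effect of sex/gender and other modulator variables (age, disease duration, medication, lifestyle, mood" and extends to response to treatment.
- Section 4 states that "we aim to assess the influence of sex/gender in tDCS treatment efficacy and central pain modulation mechanisms" and sets a floor for men: "whereas males will represent at least the 30% of the selected patients, in order to improve and facilitate subsequent comparative analysis".
- Section 4 also gives the wish to estimate the effect by ICD-11 pain category as one reason for enlarging the sample from 21 to 120.

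The other analyses in Section 7 that mention subgroups or modifiers are these:

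- The efficacy model is a repeated-measures ANOVA with two factors, time (pre, post) and arm (tDCS, tACS, sham).
- Covariates are added if they correlate with outcome: "These potential covariates are basically age, self-perceived stress, social support, catastrophism and medication intake".
- Simple ANOVAs compare the CPM, TSSP and EEG indexes "between specific groups of patients, divided by type/origin of chronic pain and sex".
- Linear and logistic regressions use baseline CPM, TSSP and EEG to predict improvement.

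**The concern.** To ask whether a treatment works better in one sex or one pain condition is to ask whether two effects differ. Running the same test in each group answers a different question: whether each group, taken alone, shows an effect. The result of each separate test depends heavily on group size, and the groups here are unequal by design. A true effect common to all patients can easily be significant in the larger group and not in the smaller one.

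The plan gives no rule for comparing the separate results, so nothing prevents that pattern from being reported as a sex- or diagnosis-specific effect. At stake are the treatment-response part of objective H and the sex aim in Section 4. The whole-sample comparison of the three arms is not at stake.

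**Working it through.** **1. Is there a formal comparison anywhere?** No.

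- Time x arm in the main ANOVA tests the overall effect.
- Age and medication intake are possible covariates. Adjusting for them does not test whether they change the arm effect. Sex, pain type and duration are not on the covariate list.
- The ANOVAs by sex and pain type compare biomarker indexes, not response by arm. They do serve the biomarker part of objective H.
- The regressions state no arm-by-predictor term.

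**2. The plan's own figure.** Section 4 gives 21 patients for three groups, two measurements, an effect of 0.68 labelled F, alpha 0.01 and power 0.99. Take 0.68 as Cohen's f and assume a pre-post correlation of 0.5 (not stated). The noncentrality is then f² × N × 2/(1 − 0.5) = 0.4624 × 21 × 4 = 38.84 on 2 and 18 df, and power is 0.994 (0.976 at N = 18). So 21 reproduces, but for the whole-sample time x arm test only.

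**3. Expected cells.** Inputs: N = 120 (Section 4), 40/40/20 allocation (Section 3), about 70% women (Section 4). No dropout is applied, and the sexes are assumed balanced across arms.

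- Women: 84 × 0.4, 0.4, 0.2 = 33.6 / 33.6 / 16.8
- Men: 36 × 0.4, 0.4, 0.2 = 14.4 / 14.4 / 7.2

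**4. Power within each sex when the effect is identical.** With two time points, the plan's test equals a one-way ANOVA on change. Let both active arms differ from sham by d, in SDs of change (assumed). The noncentrality is λ = n × 0.8 × 0.2 × d² = 0.16 n d², so 13.44 d² in women (2, 81 df) and 5.76 d² in men (2, 33 df). At d = 0.68, λ is 6.215 and 2.663.

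The chance that exactly one sex is significant is pW(1 − pM) + pM(1 − pW). At d = 0.68 and alpha 0.05 this is 0.583 × 0.733 + 0.267 × 0.417 = 0.539.

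| d (assumed) | Alpha 0.05: women / men | Exactly one | Alpha 0.01: women / men | Exactly one |
|---|---|---|---|---|
| 0.34 | 0.178 / 0.099 | 0.242 | 0.059 / 0.026 | 0.082 |
| 0.5 | 0.344 / 0.161 | 0.394 | 0.151 / 0.050 | 0.186 |
| 0.68 | 0.583 / 0.267 | 0.539 | 0.336 / 0.101 | 0.369 |
| 1.0 | 0.907 / 0.525 | 0.480 | 0.752 / 0.274 | 0.614 |
| 2.0 | 1.000 / 0.989 | 0.011 | 1.000 / 0.941 | 0.059 |

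With 20% dropout (assumed) in every cell, "exactly one" becomes 0.339 and 0.490 at alpha 0.05, and 0.142 and 0.284 at alpha 0.01, for d = 0.5 and 0.68.

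If 0.68 is read literally as f, then f on the change scale is 0.68 × √4 = 1.36. Under 40/40/20 allocation the arm means have an SD of d × √(0.8 × 0.2) = 0.4d, so d = 1.36/0.4 = 3.4, and the chance is about 0.

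**5. The interaction test under the same conditions.** In a simulation of 40,000 trials with whole-number cells (34/34/17 and 14/14/7) and identical effects, the 2-df arm x sex test was significant in 4.9% to 5.2% at alpha 0.05 and in 0.95% to 1.01% at alpha 0.01. The same simulation gave 0.395 and 0.543 (alpha 0.05) and 0.190 and 0.373 (alpha 0.01) for "exactly one" at d = 0.5 and 0.68, close to the table.

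**6. What the interaction test can detect.** For a difference δ between the sexes, λ = δ²/(1/13.44 + 1/5.76) = 4.032 δ² on 2 and 114 df.

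- Effect of 0.68 SD in women and 0 in men: λ = 1.864, power 0.208 (alpha 0.05) and 0.074 (alpha 0.01).
- Effect of 0.5 SD in women and 0 in men: power 0.131 and 0.039.
- Difference needed for 80% power: 1.57 SD and 1.89 SD.

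**7. Pain type.** The types are not enumerated, so their cells cannot be computed; there are only 120 × 0.2 = 24 sham patients in total. As an illustration, with 3 to 6 equal types (assumed) and an identical effect of 0.68 SD, the types would not all agree in significance in 62% to 64% of trials at alpha 0.05 and 24% to 31% at alpha 0.01.

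**The case against.** The gap itself is not in dispute, but five points can fairly be made.

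- **The plan never says that one significant and one non-significant result means dependence.** Section 4 speaks of effect sizes by pain type, which is the language of estimation. This stands in part: the percentages above are conditional on that reading. The plan neither adopts it nor excludes it, and separate estimates still describe rather than test.
- **The only alpha in the document is 0.01.** There the range for 0.5 to 0.68 SD is 19% to 37%, or 14% to 28% with 20% dropout. This stands, and both alphas are shown. The figure is not always lower at 0.01: at 1.0 SD it is 61% against 48%.
- **Under the effect size that reproduces 21, the risk is about 0.** This is correct arithmetic, but it needs a difference of about 3.4 SD of change. Even then, two significant results cannot say whether the effects differ.
- **An interaction test has little power here.** True. It shows that this trial can support few claims of dependence, which is a reason to say in advance what would justify one.
- **The nominal error is per test, and an ANOVA term does not cover the responder chi-square tests.** Both stand. Table 1 lists 14 endpoint domains. With three factors that is 42 tests and about 42 × 0.05 = 2.1 expected false positives (0.42 at alpha 0.01). The fix below takes account of this.

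**Conclusion.** The concern holds. The plan sets out to learn whether the treatment effect depends on sex or diagnosis, and its only stated method cannot answer that.

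If differing significance is taken as dependence, an identical effect of 0.5 to 0.68 SD of change would look like a sex difference in 39% to 54% of trials at alpha 0.05 and 19% to 37% at alpha 0.01. The interaction test would do so in 5% and 1%. These sizes rest on assumed effects in SDs of change, equal benefit of both active arms, an exact 70/30 split balanced across arms, and no dropout. The missing comparison does not depend on any of these assumptions.

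The change should be made, but the matter concerns a secondary objective and leaves the whole-sample primary analysis intact.

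**What to change.** In Section 7, state that:

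- dependence of the treatment effect on sex, pain type or duration will be claimed only on the arm x time x subgroup term (equivalently, arm x subgroup on change) in the whole-sample three-group model, one factor at a time, at a stated alpha;
- effects within subgroups will be reported as estimates with confidence intervals and labelled exploratory;
- the number of interaction tests will be reported, preferably with the endpoints to be tested limited in advance;
- the open-ended reference to further characteristics is replaced by a fixed list, with the pain-type and duration categories defined.

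For responder outcomes, an arm x subgroup term in a logistic model would be a useful addition. Without it, responder results by subgroup should stay descriptive.

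The cost is wording in the analysis plan; no new data are needed. The drawback is low power: most subgroup statements will be wide-interval estimates. The gain is protection against overclaiming, not a firm answer on effect modification.

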(Adams & Turk, 2015; Keefe et al., 2004; Jensen et al., 2011). Thus, these factors must be taken into account when assessing the efficacy of tES intervention and we intend to account them as covariates in statistical analysis.

Changes observed in criteria variables between pre- and post-evaluation must be equal or higher than the 30%, in order to ensure their clinical significance. It means that the improvement observed in self-reported questionnaires and in sensory testing (except for EEG) have to achieve or surpass the 30% of the original outcome. The direction of these differences depends on the specific scale; for example, it is expected a reduction in the global MPI score after treatment, but also a rise in pain thresholds. In the case of EEG, the analysis pre-post treatment are only subjected to the statistical significance. However, changes in brain activity patterns attributed to the tES will be tried to relate with improvement in clinical features.

Although all explained measurements are considered as success criteria of treatment, we selected pain intensity as the primary end point, taken as the average obtained from daily numerical rating scale. In this sense, participants will be classified into responders when they report, at least, a 30% decrease in their pain intensity. The rest of the variables are taken as secondary end points and are also regarded as treatment-efficacy indexes, basically the pain thresholds, life quality, physical functioning, interference caused by pain, pain unpleasantness, sleep quality, depression/anxiety, fatigue, caregiver burden and CPM/TSSP responses.

Table 1: End points of the clinical trial and their respective evaluation instruments

End points		Assessment tools
Primary end point	Pain intensity	Numerical Rating Scale of eleven points (0-10 NRS). Average obtained from daily self-reports during the fifteen days before treatment and the fifteen days after treatment.
Secondary end points	Global severity of chronic pain syndrome	Global and subscales scores of Multidimensional Pain Inventory (MPI).
	Interference caused by pain in daily living	Subscale score of Multidimensional Pain Inventory (MPI). Numerical Rating Scale of eleven points (0-10 NRS). Average obtained from daily self-reports during the fifteen days before treatment and the fifteen days after treatment.

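### The regressions meant to show that baseline CPM, TSSP and EEG predict treatment efficacy name no treatment arm and no biomarker-by-arm interaction, so their slopes cannot separate prediction of tES benefit from prognosis or placebo response

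*Combined protocol and SAP*

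**What the plan says.** The hypothesis in section 2 is that "central biomarkers of pain processing and modulation (i.e., CPM, TSSP and EEG) will be useful to predict the patient response to treatment" and so the efficacy of the tES procedures. Objective G repeats this aim and adds the identification of the best responders.

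Section 7 carries it out. Baseline CPM, TSSP and EEG "are also regarded as potential predictors of the treatment efficacy". To test this, the plan says that "the pre-treatment indexes of these biomarkers will be used as independent variables in" a set of linear regressions. Their outcome is fixed by a further clause, "which includes the clinical improvement in each endpoint as dependent measure". The procedure is then repeated by logistic regression, "establishing the respondent vs. no-respondent categories as dichotomic variable". Section 7 defines a respondent as a participant with at least 30% pre-to-post improvement, whatever the arm, so a sham patient can be one.

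Three other statements could bear on what enters these models:

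- Section 6.2, on social support, stress, catastrophizing and beliefs about control of pain: "we intend to account them as covariates in statistical analysis".
- Objective H, on the effect of sex/gender and other modulators: "age, disease duration, medication, lifestyle, mood...) on all the analyses".
- Section 7, after the ANOVA: "All these statistical analyses will be repeated in separated groups of patients, created in the basis of sex, type and duration of chronic pain". The list of grouping variables is left open.

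None of them names treatment arm, a biomarker-by-arm term or a contrast with sham for the predictor regressions. Where section 7 does intend to compare arms, it says so: in the repeated-measures ANOVA and in the chi-square comparison of responders.

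**The concern.** Efficacy in a sham-controlled trial is a contrast between active and sham. A predictor of efficacy is therefore a baseline variable along which that contrast changes, which means the biomarker slope differs between arms. The planned outcome is each patient's own improvement, which mixes tES benefit with natural course and placebo response. A biomarker that forecasts improvement equally well under sham would still give a significant slope, and on the plan's wording it could be reported as a predictor of tES efficacy.

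At stake are the second part of the main hypothesis and objective G. The sham arm that could resolve the ambiguity is already in the design, but the regressions as described do not use it for that purpose.

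**Working it through.** **The plan's own figure.** Section 4 gives 21 patients for a repeated-measures ANOVA (three groups, two measurements, effect 0.68, alpha 0.01, power 0.99). With an assumed pre-post correlation of 0.5, lambda = 0.68² × 21 × 2 / (1 − 0.5) = 38.8 on 2 and 18 df. This gives power 0.994 at N = 21 and 0.976 at N = 18, so the figure reproduces. It covers the group-by-time test only. The documents give no sample size, power or alpha for the predictor regressions.

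**Inputs from the documents.** N = 120 (section 4), allocated 40:40:20 (section 3): 48 tDCS, 48 tACS, 24 sham, so 96 active. Alpha 0.01 is the only level stated; 0.05 is used here as a conventional assumption.

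**What each slope estimates.** Let improvement in an arm be a constant + β × biomarker + error, with randomisation balancing the biomarker across arms.

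- All patients pooled, with or without an arm main effect: about 0.8 × β(active) + 0.2 × β(sham).
- Active patients only: β(active).
- Biomarker × arm: β(active) − β(sham).

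Only the last is zero when the biomarker carries no information on tES benefit, that is, when the slope is the same in every arm.

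**Illustration.** Assumptions: correlation r between biomarker and improvement identical in all arms, an active shift of 0.68 SD, no dropout, 10,000 simulated trials. Percentage of trials with a significant result:

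| Model | r = 0.3, alpha 0.05 | r = 0.3, alpha 0.01 | r = 0.2, alpha 0.05 |
|---|---|---|---|
| Pooled 120, no arm | 90 | 75 | 56 |
| 96 active only | 85 | 67 | 50 |
| Pooled, arm added, no interaction | 92 | 78 | 59 |
| Biomarker × arm | 5 | 1 | 5 |

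Hand check at r = 0.3 and alpha 0.05, using power ≈ Φ(atanh(r) × √(n − 3) − 1.96):

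- Active only: 0.3095 × √93 = 2.985 and Φ(1.025) = 0.85.
- Pooled without arm: the shift dilutes r to 0.3 / √(1 + 0.68² × 0.8 × 0.2) = 0.29. Then 0.298 × √117 = 3.22 and Φ(1.26) = 0.90.

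A different set-up (residual SD 1, shift 0.5 SD, 4,000 trials) gives 57% and 89% for pooled slopes of 0.2 and 0.3, and about 5% for the interaction. With an assumed 20% dropout (77 active, 19 sham) and r = 0.3, the figures are 83% pooled and 5% interaction. A logistic version, with assumed response of 20–30% on sham and 40–50% on active, gives 70–73% pooled and 2–3% interaction.

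**Precision of the interaction** (residual SD 1, biomarker SD 1, alpha 0.05):

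- All active vs sham: SE = √(1/96 + 1/24) = 0.228. Slope difference for 80% power = 2.80 × 0.228 = 0.64. Power at 0.3 = Φ(0.3/0.228 − 1.96) = 0.26. Simulated with baseline in the model: half-width 0.47, power 25% at 0.3, 80% at 0.68.
- One technique vs sham: SE = √(1/48 + 1/24) = 0.25. Slope difference for 80% power = 0.70 (0.75 simulated). Power at 0.3 is 21–22%, half-width 0.52.
- 77 vs 19: SE = 0.256, half-width 0.53, power at 0.3 of 20–22%.

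**Number of tests.** Table 1 has 14 end-point rows (1 primary, 13 secondary). 14 × 3 biomarkers × 2 model types = 84, counting EEG as one index and each row as one measure. Leaving out the satisfaction row, which has no baseline, gives 13 × 3 × 2 = 78. Several rows hold more than one instrument, so the real number is likely higher. If every null holds, 84 × 0.05 = 4.2 chance findings are expected. That is a mean and not a ceiling: with independent tests, more than 4 occur about 41% of the time.

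**The case against.** **The text does not exclude an arm term.** True. A reader might infer that the plan rules one out, but it is only silent. An unstated term is still not pre-specified, and an arm main effect alone would not help, as the third row of the table shows.

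**Biomarker groups may be meant.** Section 7 defines CPM and TSSP respondent groups and possible clusters, and the list of subgroups for the repeated ANOVAs is open-ended. Running the three-arm ANOVA within biomarker groups is a possible reading and would give arm comparisons in each stratum. It is not stated, and separate tests in strata still do not test whether the treatment effect differs between them. This softens the point without removing it.

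**Forecasting who improves on tES needs no interaction.** Correct. The introduction speaks of predicting outcomes with tES, and objective G also seeks best responders. The regressions can serve that narrower aim. The fault lies in the claim about efficacy, which sections 2 and 7 both make.

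**The corrected test is weak.** It is, with 24 sham patients. That supports reporting an interval and calling the analysis exploratory. It does not support resting the efficacy claim on a better-powered test of a different question.

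**The percentages are assumed, not observed.** A reader might take 85–92% as this trial's false-positive rate. The documents give no correlation between any biomarker and improvement. These rates are simply the power to detect the assumed correlation; they show the ambiguity, not that it will arise.

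**Conclusion.** The point stands as a specification gap that should be closed. As described, the regressions can show who improves, but they cannot show that a biomarker predicts benefit from tES. Pooled, active-only and arm-adjusted slopes all share the limitation. This conclusion follows from the form of the models. The sizes (50–92% against about 5% at alpha 0.05) depend on assumed correlations of 0.2–0.3, equal slopes in all arms and a 0.68 SD shift.

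Three wider conclusions are not supported:

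- A reader might infer that the patient profiles of objective B rest on this slope. Section 7 builds those from biomarker clusters and respondent groups, not from improvement regressions.
- A reader might add that regression to the mean will itself create false predictors. The linear models leave improvement undefined and the documents give no pre-post correlation, so no size can be attached to this.
- A reader might extend the criticism to the efficacy results. The repeated-measures ANOVA and the responder chi-square compare arms and are unaffected.

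**What to change.** For NRS pain intensity, the primary end point, include all randomised arms and fit:

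post-treatment score = baseline score + biomarker + arm + biomarker × arm

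with a logistic version as supportive. Report the interaction with its 95% confidence interval for tDCS vs sham and for tACS vs sham, and for pooled active vs sham if a common slope is assumed.

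The sponsor should name the main contrast in advance. Objectives E and F treat the two techniques separately, and the choice matters. If a slope of 0.5 existed only under tACS, simulated power is 17% for the pooled contrast and 48% for tACS vs sham. If both techniques share a slope difference of 0.3, pooling is slightly better (about 25% against 21%).

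Rest any claim of predicting tES efficacy on the interaction, and label slopes without it as prognostic. Label the whole analysis exploratory and state the number of tests (at least about 84 as planned, with about 4 expected by chance at alpha 0.05 if all nulls hold, and possibly more).

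The cost is three added terms with active arms pooled (baseline, arm, interaction), or five with three arms (1 + 2 + 2), on data already collected. The price is imprecision: a null interaction must not be read as evidence of no prediction. The logistic interaction would rest on about 5–7 sham responders (24 × 20–30%, assumed). Fewer biomarkers are likely to be declared predictive.
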